6. DOSE MODIFICATIONS

If toxicity occurs, the toxicity will be graded utilizing the NCI CTCAE v4.0, and appropriate supportive care treatment will be administered to decrease the signs and symptoms thereof. Dose adjustments will be based on the organ system exhibiting the greatest degree of toxicity.

6.1 Dose Modifications Due to Hematologic Toxicity

Dose reductions or holds and initiation of supportive care are allowed as clinically indicated by the treating physician. Patients whose treatment is delayed due to toxicity will discontinue study drug or will proceed with the next cycle of treatment when toxicity has improved (as long as the toxicity resolves within 3 weeks) according to the dose modifications below. Two dose reductions for toxicity will be allowed. In addition, dose reductions will also be allowed based on clinical judgment of the treatment physician. If persistent toxicity occurs despite two dose reductions, the patient will be removed from the study.

Patients who require a treatment delay of more than 3 weeks due to treatment-related toxicity will be discontinued from study treatment, unless the treating physician and the Medical Monitor agree that continued treatment at lower doses is in the best interest of the patient.

Table 1 Regorafenib Dose Levels for Dose Modifications due to Toxicities

Dose Level	Regorafenib ^a
0	160 mg orally once daily
-1	120 mg orally once daily
-2	80 mg orally once daily

^a Two dose reductions are allowed for regorafenib. Patients who require more than two dose reductions due to toxicity will be discontinued from the study.

The regorafenib dose modifications for hematologic toxicities are below in Table 2.

CONFIDENTIAL

STUDY DEVICE: SIR-Spheres®

SCRI INNOVATIONS STUDY NUMBER: GI 189

DATE OF ORIGINAL PROTOCOL: 16 December 2013

Version 2.0

Date of Amendment #1: 15 April 2014

Table 2 Regorafenib Dose Modifications for Hematologic Toxicities

Toxicity	Regorafenib Dose ^a
Grade 3 And Recurrence of Grade 3	Hold dose until recovery to \leq Grade 2, then resume regorafenib at one lower dose level.
Grade 4	Hold dose until recovery to \leq Grade 2, then resume regorafenib at one lower dose level, or discontinue at the discretion of the investigator after discussion with the Medical Monitor.

^a Any patient who requires a treatment delay of more than 3 weeks due to treatment-related toxicity will be discontinued from study treatment, unless the treating physician and the Medical Monitor agree that continued treatment at lower doses is in the best interest of the patient.

6.2 Regorafenib Dose Modifications for Non-Hematologic Toxicity

6.2.1 Regorafenib Dose Modifications for Abnormal Liver Function Tests

Regorafenib has been associated with severe drug-induced liver injury with fatal outcome in previous studies. Liver function tests (LFTs) will be monitored during study treatment as described in **Error! Reference source not found.** Appendix A and **Error! Reference source not found.** Appendix B. Dose modifications for regorafenib are recorded in Table 3 below.

Table 3 Regorafenib Dose Modifications for Abnormal Liver Function Tests

Toxicity	Regorafenib Dose
Baseline - Grade 1 And Recurrence OR Baseline Grade 1 – Grade 2 And Recurrence	Treat on time and check AST, ALT and bilirubin 2x/week for 2 weeks followed by weekly assessments for at least 4 weeks.
Baseline - Grade 2	Hold dose until \leq Grade 1 and check AST, ALT and bilirubin 2x/week. Resume regorafenib at 1 lower dose level and check AST, ALT, bilirubin 2x/week for 2 weeks followed by weekly assessments for at least 4 weeks. ^a
Recurrence of Baseline - Grade 2	Discontinue regorafenib ^b .
Baseline Any Grade-Grade 3	Hold dose until \leq Grade 1 for baseline - Grade 1 OR until Grade 2 if baseline was Grade 2.

CONFIDENTIAL

STUDY DEVICE: SIR-Spheres®

SCRI INNOVATIONS STUDY NUMBER: GI 189

DATE OF ORIGINAL PROTOCOL: 16 December 2013

Version 2.0

Date of Amendment #1: 15 April 2014

	Check AST, ALT and bilirubin 2x/week.
	Resume regorafenib at 1 lower dose level and check AST, ALT, bilirubin 2x/week for 2 weeks followed by weekly assessments for at least 4 weeks. ^a
	Note: If ALT or AST >8 x ULN with a concomitant rise in bilirubin (of any degree) compared to previous bilirubin values, consider permanent discontinuation at the first occurrence ^b .
Recurrence of Baseline Any Grade-Grade 3	Discontinue regorafenib ^b .
Baseline Any Grade-Grade 4	Discontinue regorafenib ^b

^a If all values remain stable for 2 full cycles, dose re-escalation may be considered at the discretion of the investigator. After re-escalation AST, ALT, and bilirubin should be checked 2x/week for 2 weeks, followed by weekly assessments for at least 4 weeks.

^b In case of discontinuation, AST, ALT, and bilirubin should be checked 2x/week for 2 weeks, followed by weekly assessments until recovery to baseline.

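### Read literally, Table 3 stops regorafenib for a second Grade 2 liver event but allows resumption at 80 mg when that second event is first seen at Grade 3 (normal baseline, no other dose reduction)

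*Protocol*

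**What the plan says.** Table 3 in Protocol Section 6.2.1 sorts liver events by baseline grade, event grade and whether the event is a recurrence.

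- **Baseline Grade 1 rising to Grade 2** has its own entry, "Baseline Grade 1 – Grade 2 And Recurrence". Dosing continues on time with extra liver tests.
- **Baseline to Grade 2, no baseline grade written.** Hold until Grade 1 or lower, then resume one dose level lower. The matching recurrence row, "Recurrence of Baseline - Grade 2", says to discontinue.
- **"Baseline Any Grade-Grade 3"**. Hold, then resume one level lower. The recovery target is Grade 1 or lower, or "until Grade 2 if baseline was Grade 2". The row does not mention an earlier Grade 2 event. When ALT or AST exceeds 8 x ULN with a rise in bilirubin, a note says to "consider permanent discontinuation at the first occurrence".
- **"Recurrence of Baseline Any Grade-Grade 3"**. Discontinue.
- **Grade 4 from any baseline.** Discontinue.

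After a resumption, Table 3 requires AST, ALT and bilirubin twice weekly for 2 weeks and then weekly for at least 4 weeks. Footnote a adds: "If all values remain stable for 2 full cycles, dose re-escalation may be considered at the discretion of the investigator".

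Table 1 in Section 6.1 sets the dose levels at 160, 120 and 80 mg and allows two reductions. A patient who needs a third is discontinued.

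**The concern.** A dose-modification table should not respond more gently as the event gets worse. Each recurrence row here names its own grade, so a patient who has already had a Grade 2 event can move into a row that does not count it. A second event at Grade 2 then ends regorafenib, while one at Grade 3 permits another attempt at a lower dose.

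The setting makes this worth correcting. Section 6.2.1 opens with "Regorafenib has been associated with severe drug-induced liver injury with fatal outcome in previous studies", and these patients also receive radiation to the liver. Safety is the primary objective. Section 10.4.4 summarizes adverse events leading to discontinuation, and the SAP tabulates treatment modifications and discontinuations with their reasons. If some investigators follow the Grade 3 row as written and others treat Grade 3 as at least a Grade 2 recurrence, the same clinical course could be handled and counted differently.

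**Working it through.** No sample size or error rate is involved, so the check is a trace through the table.

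**Step 1: who is in the unlabelled Grade 2 rows.** Baseline Grade 1 patients who reach Grade 2 have their own entry, so the Grade 2 rows with no stated baseline are read as normal baseline. This is an inference from the layout.

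**Step 2: trace the pairs.** The inputs are Table 1 (160 to 120 to 80 mg) and the Table 3 actions. The trace assumes normal baseline, no reduction for another toxicity and no re-escalation. In the second-event columns, the grade is the one first seen.

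| First event | Second: Grade 2 | Second: Grade 3 | Second: Grade 4 |
|---|---|---|---|
| Grade 2 (resumed at 120 mg) | stop | hold, resume at 80 mg | stop |
| Grade 3 (resumed at 120 mg) | hold, resume at 80 mg | stop | stop |

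The resumption dose is 80/160 = 50% of the starting dose.

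- Across the top row, the action goes stop, resume, stop. Grade 3 is treated more mildly than Grade 2.
- Down the Grade 2 column, a Grade 2 history leads to a stop and a Grade 3 history leads to resumption. The worse history gets the milder action.

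So 2 of the 6 pairs, (2,3) and (3,2), are each milder than (2,2). These are counts of table cells, not of patients or risk.

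**Step 3: other baselines.**

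- Baseline Grade 1, first event Grade 2: a second event leads to treat on time, then hold and resume at 120 mg, then stop, for Grades 2, 3 and 4.
- Baseline Grade 1, first event Grade 3: treat on time, stop, stop.
- Baseline Grade 2: a first Grade 3 is held and resumed; a second Grade 3, or any Grade 4, stops the drug.

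None of these is out of order.

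**Step 4: can a second event be first seen at Grade 3?** If a Grade 2 value is recorded on the way up, the Grade 2 recurrence row already requires a stop. The gap needs an event that passes Grade 2 between tests. The extra tests after resumption last at least 2 + 4 = 6 weeks. Once they end, the schedules (Sections 7.3.7, 7.3.8, 7.4.7 and 7.4.9; Appendices A and B) list a metabolic panel only on Day 1 of each 28-day cycle from Cycle 3. Day 15 is coagulation testing only. With scheduled tests 28 days apart, first detection at Grade 3 is possible.

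**Step 5: does another rule force a stop once the Grade 3 event has recovered in time?**

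- The note on values above 8 x ULN asks only for consideration.
- Section 3.3 (intolerable or irreversible toxicity) depends on judgement.
- The 3-week delay rule in Section 6.1 is not reached if recovery is timely, and it can be waived.
- The 7-day Grade 3 rule is in Section 6.3, which is headed for other toxicities. Even if applied, it spares events of 7 days or less.
- Sections 7.3.7 and 7.4.4 require eligible liver function before dosing and remove patients with persistent toxicity. A recovered patient passes.
- The rule in Sections 5 and 10.4.3 on Grade 3 liver values is met at the third related case and acts on recruitment.
- The general rule in Section 6 chooses between organ systems; it does not rank successive liver events.

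None of them forces it.

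**Step 6: the dose cap.** With one earlier reduction for another toxicity, either resumption in the grid would be a third reduction (160 to 120 to 80 mg, then none left), so Table 1 stops the drug. If footnote a had returned the patient to 160 mg, resumption would be at 120 mg, and the action would still be milder than a stop.

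**The case against.** The best counter-argument is that two rows can apply to the same patient. Nothing in Table 3 says that worsening past an earlier Grade 2 is not a recurrence of it, and a careful clinician could treat Grade 3 as including Grade 2 and stop. Testing after resumption is frequent for at least 6 weeks, so a rising value will often be caught at Grade 2, where the drug stops anyway. The row labels are shorthand and not used uniformly. Section 8.2 also refers to the approved labelling, which may settle the sequence.

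Much of this stands. It narrows the problem to events first detected at Grade 3 and makes it likely that few patients are involved. It does not remove the problem, because the table does not state the cumulative reading and the Grade 3 row, taken alone, instructs resumption. The labelling is not in these documents, so whether it resolves the sequence is unknown.

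A reader might infer that every patient who goes from Grade 2 to Grade 3 is put back on regorafenib, or that nothing in the protocol would stop such a patient. The documents do not support either. The Grade 2 recurrence row stops the drug whenever a second Grade 2 is recorded, the investigator may stop under Section 3.3, and the dose cap stops anyone with an earlier reduction for another toxicity.

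**Conclusion.** The inconsistency is real on a literal reading and is a minor safety-rule correction. It affects patients with normal baseline liver tests and no other dose reduction. After a Grade 2 event resumed at 120 mg, a second Grade 2 means stop, while an event first seen at Grade 3 allows resumption at 80 mg. The companion inversion, Grade 3 then Grade 2, also resumes at 80 mg. Baseline Grade 1 and Grade 2 patients are not affected.

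The conclusion rests on reading the unlabelled Grade 2 rows as normal baseline, on the second event escaping detection at Grade 2, and on recovery in time. The documents give no liver-event rates, so the number affected cannot be estimated; it is probably small.

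It would be tempting to conclude that the trial's safety results or its stopping rules are compromised. The documents do not support that: the study-level rules count related cases whatever the patient's later dosing, and no analysis depends on this row.

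**What to change.** Add one sentence to Table 3: *For patients with normal baseline liver tests, a Grade 3 event after an earlier Grade 2 event that led to a hold and dose reduction counts as a recurrence: discontinue regorafenib.* Add *except as above* to the Grade 3 hold-and-resume row. Leave the rules for baseline Grade 1 and baseline Grade 2 unchanged.

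This turns one of the six pairs, (2,3), into a stop. It leaves (3,2), so the table should also state whether Grade 2 after an earlier Grade 3 counts as a recurrence. Without that statement the second inversion remains.

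Before amending, the sponsor should check the labelling cited in Section 8.2. If resumption at 80 mg is intended, saying so would at least remove the ambiguity.

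The cost is a small text change to one table, with no added visits, tests or patients. The downside is that a few patients would stop regorafenib sooner.

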6.2.2 Regorafenib Dose Modifications for Hand-Foot Skin Reaction

Hand-foot skin reaction is a known adverse event for regorafenib. The dose modifications are provided in Table 4 below.

Table 4 Regorafenib Dose Modifications for Hand-Foot Skin Reaction

Toxicity	Regorafenib Dose
Grade 1	
Numbness, dysesthesia, paraesthesia, tingling, painless swelling, erythema or discomfort of the hands or feet which does not disrupt the patient's normal activities
 
Institute supportive measures immediately for symptomatic relief and continue treatment with the same dose level.

Grade 2	
First and Second Occurrence -
 
Institute supportive measures immediately for symptomatic relief and decrease regorafenib one dose level (see Table 1)
 
 • If toxicity does not return to Grade 0-1 despite dose reduction, interrupt regorafenib for a minimum of 7 days until toxicity has resolved to Grade 0-1^a. • If no improvement after 7 days, continue to hold until toxicity has resolved to Grade 0-1^{a,b}. • When resuming treatment after a dose interruption, reduce regorafenib an additional dose level^a.

CONFIDENTIAL

STUDY DEVICE: SIR-Spheres®

SCRI INNOVATIONS STUDY NUMBER: GI 189

DATE OF ORIGINAL PROTOCOL: 16 December 2013

Version 2.0

Date of Amendment #1: 15 April 2014

Patients requiring >2 dose reductions will discontinue	
Grade 3 Moist desquamation, ulceration, blistering or severe pain of the hands or feet, or severe discomfort that causes the patient to be unable to work or perform activities of daily living	First and Second Occurrence - Institute supportive measures immediately for symptomatic relief and interrupt regorafenib for a minimum of 7 days and until toxicity resolved to Grade 0-1 (see Table 1). 
 When resuming treatment after dose interruption, decrease regorafenib by one dose level^a. Patients requiring >2 dose reductions will discontinue protocol therapy.

^aIf toxicity returns to Grade 0-1 after dose level reduction, dose re-escalation is permitted at the discretion of the investigator

^bIf no recovery after 3 weeks of holding drug, patients should go off study unless in the opinion of the investigator & SCRI Innovations Medical Monitor, there is reason to believe that the patient is still experiencing clinical benefit.

The following supportive measurements should be considered for prevention and treatment of hand-foot skin reaction:

Control of callouses:

Before initiating treatment with regorafenib -

- Check condition of hands and feet
- Suggest a manicure/pedicure, when indicated
- Recommend pumice stone use for callous or rough spot removal

During regorafenib treatment -

- Avoid pressure points
- Avoid items that rub, pinch or create friction

Use of creams:

The following non-urea based creams should be applied liberally - Cetaphil, Aveeno, Udderly Smooth, Gold Bond, Norwegian Formula, and Eucerin.

The following keratolytic creams should be used sparingly and only to affected (hyperkeratotic) areas - urea-based creams and salicylic acid 6%.

Approximately 5-8% of A-hydroxy acids-based creams provide gentle chemical exfoliation. These creams should be applied liberally two times each day.

Topical analgesics like lidocaine 2% to be considered for pain control.

Topical corticosteroids like clobetasol 0.05% should be considered for subjects with Grade 2 or 3 hand-foot skin reaction. Avoid systemic steroids.

Cushions:

Protect tender areas by doing the following -

- Use socks/gloves to cover moisturizing creams
- Wear well-padded footwear
- Use insole cushions or inserts (e.g., silicon, gel)

CONFIDENTIAL

STUDY DEVICE: SIR-Spheres®

SCRI INNOVATIONS STUDY NUMBER: GI 189

DATE OF ORIGINAL PROTOCOL: 16 December 2013

Date of Amendment #1: 15 April 2014

Version 2.0

- Foot soaks with tepid water and Epsom salts

6.2.3 Regorafenib Dose Modifications for Hypertension

The dose modification table for treatment-emergent hypertension should be followed. Blood pressure measurements will be followed closely and appropriate treatment to effectively control hypertension is highly recommended.

CONFIDENTIAL

STUDY DEVICE: SIR-Spheres®

SCRI INNOVATIONS STUDY NUMBER: GI 189

DATE OF ORIGINAL PROTOCOL: 16 December 2013

Date of Amendment #1: 15 April 2014

Version 2.0

Table 5 Regorafenib Dose Modifications for Hypertension

Toxicity	Antihypertensive Therapy	Regorafenib Dose
Grade 1 Prehypertension (systolic BP 120 – 139 mm Hg or diastolic BP 80 - 89 mm Hg)	None	No dose modification. Increase blood pressure monitoring.
Grade 2 Systolic BP 140 – 159 mm Hg or diastolic BP 90 -99 mm Hg, OR Symptomatic increase by >20 mm Hg (diastolic) if previously within normal limits	Treat with the aim to achieve diastolic BP \leq 90 mm Hg: If BP previously within normal limits, start antihypertensive monotherapy. If patient already on anti-hypertensive medication, titrate up the dose.	No dose modification. If symptomatic, hold regorafenib until symptoms resolve AND diastolic BP \leq 90 mm Hg ^a . When regorafenib is restarted, continue at the same dose level.
Grade 3 Systolic BP \geq 160 mm Hg or diastolic BP \geq 100 mm Hg OR More than one drug or more intensive therapy than previously used indicated	Treat with the aim to achieve diastolic BP \leq 90 mm Hg: Start antihypertensive medication. AND/OR Increase current antihypertensive medication AND/OR Add additional antihypertensive medications.	Hold regorafenib until diastolic BP \leq 90 mm Hg, and if symptomatic, until symptoms resolve ^a . When regorafenib is restarted, continue at the same dose level. If BP is not controlled with the addition of new or more intensive therapy, reduce by 1 dose level ^b . If Grade 3 hypertension recurs despite dose reduction and antihypertensive therapy, reduce another dose level ^c .
Grade 4 Life-threatening consequences (e.g. Malignant hypertension, transient or permanent neurologic deficit, hypertensive crisis)		Discontinue treatment.

^a Subjects requiring a delay of > 4 weeks should go off protocol therapy

^b If blood pressure remains controlled for at least one full cycle, dose re-escalation is permitted at the investigator's discretion.

^c Subjects requiring > 2 dose level reductions should go off protocol therapy

CONFIDENTIAL

STUDY DEVICE: SIR-Spheres®

SCRI INNOVATIONS STUDY NUMBER: GI 189

DATE OF ORIGINAL PROTOCOL: 16 December 2013

Date of Amendment #1: 15 April 2014

Version 2.0

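### Protocol Table 5 tells sites both to continue and to hold regorafenib in an asymptomatic patient whose existing antihypertensive must be raised (systolic below 160, diastolic above 90 and up to 99 mm Hg)

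*Protocol*

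**What the plan says.** Protocol Section 6.2.3 sets the handling of treatment-emergent hypertension in Table 5. Two rows matter.

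- **Grade 2 row.** Entry is by "Systolic BP 140 – 159 mm Hg or diastolic BP 90 -99 mm Hg", or by "Symptomatic increase by >20 mm Hg (diastolic) if previously within normal limits". For a patient already treated, the antihypertensive column says "If patient already on anti-hypertensive medication, titrate up the dose". The regorafenib column begins "No dose modification. If symptomatic, hold regorafenib until symptoms resolve AND diastolic BP", with 90 mm Hg or below as the threshold. In this row, then, only symptoms lead to a hold.
- **Grade 3 row.** Entry is by systolic pressure of at least 160 or diastolic of at least 100 mm Hg, or, joined by OR, by "More than one drug or more intensive therapy than previously used indicated". The antihypertensive column includes "Increase current antihypertensive medication" among its options. The regorafenib column begins "Hold regorafenib until diastolic BP", again with 90 mm Hg or below as the threshold; any symptoms must also have resolved. Drug restarts at the same level, but a reduction can follow: "If BP is not controlled with the addition of new or more intensive therapy, reduce by 1 dose level".

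A footnote attached to the holds in both rows takes a patient off protocol therapy if the delay exceeds 4 weeks.

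Grading of adverse events is set elsewhere. The opening of Section 6 and Section 11.1.5 name NCI CTCAE v4.0, and Section 10.4.4 names v4.03.

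**The concern.** Raising the dose of a current antihypertensive is, on an ordinary reading, more intensive therapy than was used before. The therapy criterion in the Grade 3 row carries no pressure threshold, so a patient who is up-titrated under the Grade 2 row can meet the Grade 3 definition through that up-titration alone. The Grade 3 row also lists the same act, increasing the current drug, as part of its own management.

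The two rows then disagree on regorafenib, and two sites following the table in good faith could treat the same patient differently. Safety is the primary objective, and SAP Table 3 reports how many patients had each treatment modification and why. Part of that count would reflect which row a site happened to read. Only the Grade 3 row leads on to a dose-level reduction, and an extra hold also starts the 4-week limit on delay.

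Such patients are foreseen. Exclusion criterion 14 has patients above its limits controlled with medication before treatment starts, and the Grade 2 row itself starts monotherapy in patients whose pressure was previously normal.

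**Working it through.** The plan gives no figure to reproduce here, and the study has no formal hypothesis test (Section 10.2). The check is to apply both rows to the same patient and then look for a rule that chooses between them.

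**Step 1: apply both rows.** In each case the patient is already on one antihypertensive and needs it raised.

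| Case | BP (mm Hg) | Symptoms | Grade 2 row | Grade 3 row | Result |
|---|---|---|---|---|---|
| a | 150/95 | No | Raise the drug, regorafenib unchanged | Entered by the therapy criterion: hold until diastolic is 90 or below | Opposite instructions |
| b | 150/95 | Yes | Hold until symptoms resolve and diastolic is 90 or below | Same hold | Immediate action agrees; only Grade 3 adds a reduction path |
| c | 150/85 | No | Raise the drug, regorafenib unchanged | Release condition already met, so the hold has no duration | No practical conflict over the hold |
| d | 165/95 or 150/102 | Either | Not needed | Entered on pressure alone: hold | The therapy criterion plays no part |

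The conflict in action is therefore case (a): no symptoms, systolic below 160, diastolic above 90 and up to 99. The overlap in row labels is wider, since it also covers (b) and (c).

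**Step 2: look for a tie-break.**

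- Section 6.2.3 and the Table 5 footnotes do not rank the rows.
- The opening of Section 6 bases dose adjustment on the organ system with the worst toxicity. That ranks organ systems, not rows of one table.
- The same paragraph grades toxicity by CTCAE v4.0. It does not say how a patient who meets the written entry criteria of two Table 5 rows is to be placed.
- Section 6.3 is headed as covering other toxicities and adds no rule for hypertension.

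**Step 3: size.**

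- With 25 patients per cohort, each patient whose only hold depends on the row chosen moves the proportion with a hold by 1/25 = 4 percentage points.
- The documents do not say how many patients take antihypertensives. If 30% to 50% do (an assumption), that is 25 × 0.30 = 7.5 to 25 × 0.50 = 12.5 patients per cohort. This is a loose ceiling. It counts everyone on medication, whereas the conflict needs a patient who must be up-titrated, has no symptoms and is in the stated pressure range.

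**The case against.** The strongest reply is that the table can be read as steps: Grade 2 raises the existing drug, and Grade 3 begins when that is not enough and a heavier regimen is called for. On this view the option to increase current medication in the Grade 3 row serves patients who entered on pressure. The reading is coherent, but the table does not state it, and the words of the Grade 3 criterion do not exclude simple up-titration. The opposite assumption, that the higher grade always prevails, is not stated either, and it would leave the Grade 2 up-titration instruction with almost no patients to apply to. The ambiguity stands.

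Two other replies succeed in limiting the point.

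- **Reach.** A reader might infer that every treated patient handled under the Grade 2 row faces a contrary hold. Cases (b) and (c) show otherwise. Even in case (a), the Grade 3 row restarts drug at the same level and reduces it only if pressure is not controlled.
- **Outcome counts.** A reader might infer that the row chosen changes the number of Grade 3 or higher events in the Medical Monitor's review (Section 10.4.3) or in the summary by maximum grade (Section 10.4.4). The documents do not support that as a finding. Events are graded by CTCAE, and nothing makes Table 5 the grading instrument. Whether CTCAE itself separates these cases cannot be checked from the documents. The effect would arise only if sites graded events from Table 5's labels.

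Nor does any listed stopping rule turn on hypertension: those rules concern death, liver toxicity and bleeding. Only the undefined provision for emerging safety signals could reach it.

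**Conclusion.** The contradiction is real and narrow. For an asymptomatic patient already on antihypertensive medication who needs it raised, with systolic below 160 and diastolic above 90 and up to 99 mm Hg, Table 5 gives two regorafenib instructions that cannot both be followed, and no rule chooses between them. The conclusion rests on reading a raised dose as more intensive therapy. The table's wording permits that reading, and the Grade 3 row's own list of measures supports it.

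What is affected is whether drug is held, whether the later reduction path opens, and what SAP Table 3 counts. The number of patients cannot be estimated from the documents; the 7.5 to 12.5 per cohort above is an assumption-based ceiling and not a forecast. A shift in Grade 3 or higher event counts is a possibility only.

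**What to change.** The sponsor's clinical team should reconcile the Grade 2 and Grade 3 rows of Table 5 so that a treated, asymptomatic patient who needs up-titration in this pressure range falls in exactly one row. Which row that should be is a clinical decision, and no view is taken on it here.

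The team should also confirm that adverse events continue to be graded by NCI CTCAE as Sections 10.4.4 and 11.1.5 state, so that a Table 5 row is not used as a second grading source.

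The cost is one table edit and a confirming sentence. The SAP is dated 22 May 2018. If dosing had ended by then, which the documents do not say, the edit could no longer change treatment. The useful step would then be a note to SAP Table 3 saying that holds for hypertension may reflect either row.

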6.3 Other Regorafenib-Related Grade 3 or 4 Non-Hematologic Toxicities

The dose reduction guidelines for non-hematologic toxicities are shown in Table 6. If a Grade 3 non-hematologic toxicity that is expected to be manageable and reversible with dose reduction occurs, treatment with regorafenib should be held until the toxicity resolves to \leq Grade 1. If the Grade 3 non-hematologic toxicity lasts longer than 7 days, study drug will be discontinued. Patients with Grade 3 non-hematologic toxicity lasting \geq 7 days that does not resolve to \leq Grade 1 within 3 weeks should also be removed from the study, unless the treating physician and the Medical Monitor agree that continued treatment at lower doses is in the best interest of the patient. If a Grade 4 non-hematologic toxicity occurs, study drug will be discontinued.

If Grade 3 or 4 non-hematologic toxicity other than nausea, vomiting, or alopecia occurs, treatment with regorafenib should be held, and should be resumed at 1-level dose reduction(s) (see Table 1) as soon as the toxicity resolves to \leq Grade 1. Dose reductions will also apply for nausea and vomiting if the toxicity is Grade 3 or 4 and persists for 7 days after maximal antiemetic prophylaxis.

Table 6 Dose Modifications for Regorafenib Non-Hematologic Toxicities

Toxicity	Regorafenib Dose ^a
Grade 1 and Grade 2	No dose modifications ^a .
Grade 3 ^b	Hold dose until recovery to \leq Grade 2 (for AEs in Cycle 1: resolution to \leq Grade 1), then resume regorafenib at one lower dose level. For AEs occurring in Cycle 2 or later the investigator may consider a retreatment at the dose Level 0. If subject experiences a second Grade 3 toxicity, withhold dose until toxicity is \leq Grade 2, then reduce 1 dose level and resume treatment.
Grade 4 ^b	Discontinue treatment. For certain toxicities such as laboratory assessments (e.g., lipase increase without signs of a clinical pancreatitis), a decision about the further continuation and dose of treatment has to be determined after discussion between investigator and the sponsor.

^aThe investigator may consider lowering the regorafenib dose level in the case of Grade 1-2 toxicities which interfere with the activities of daily life, such as long lasting fatigue, anorexia, etc.

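### Table 5 starts the Grade 3 hypertension hold on systolic or diastolic pressure but releases it on diastolic alone, so an asymptomatic patient with systolic >=160 and diastolic <=90 mm Hg can be released at the reading that starts the hold

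*Protocol*

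**What the plan says.** Section 6.2.3 directs sites to follow Table 5 for treatment-emergent hypertension. The Grade 3 row has these parts:

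- **Trigger by pressure:** "Systolic BP \geq 160 mm Hg or diastolic BP \geq 100 mm Hg". A need for more than one drug, or for more intensive therapy than before, also qualifies as Grade 3.
- **Treatment aim:** "Treat with the aim to achieve diastolic BP \leq 90 mm Hg", by starting, increasing or adding antihypertensive medication.
- **Release of the hold:** "Hold regorafenib until diastolic BP \leq 90 mm Hg, and if symptomatic, until symptoms resolve". Regorafenib then restarts at the same dose level.
- **Later safeguard:** "If BP is not controlled with the addition of new or more intensive therapy, reduce by 1 dose level". Table 5 does not define when blood pressure counts as controlled.
- **Limit on delay:** under footnote a, a delay of more than 4 weeks takes the patient off protocol therapy.

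Footnote c of the schedules in Appendices A and B sets blood pressure checks weekly for the first 6 weeks of regorafenib and once per cycle after that, more often if clinically indicated.

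**The concern.** The trigger has a systolic limb and the release does not. When systolic pressure alone starts the hold and diastolic pressure is already 90 or lower, an asymptomatic patient meets the release condition from the outset. As written, that hold has no duration, and regorafenib may restart at an unreduced dose while systolic pressure is still in the Grade 3 range.

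Two things are at stake. One is the safety of these patients. The other is consistency in how often and how long regorafenib is held: sites that follow the cell literally will restart at once, and sites that use judgement will wait. Safety is the trial's primary objective, so a dose rule should not leave this open. Grading does not depend on the release rule, so adverse event grades and counts of Grade 3 or higher events do not change.

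**Working it through.** The documents give no figure to reproduce. The check is whether one reading can satisfy both trigger and release.

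**Inputs (Table 5, Grade 3 row), for an asymptomatic patient with systolic S and diastolic D in mm Hg**

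- Trigger by pressure: S >= 160 or D >= 100.
- Release as written: D <= 90.
- Release as amended: D <= 90 and S < 160.

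**Logic.** Release requires D <= 90, which rules out the diastolic limb of the trigger. Trigger and release are both true exactly when S >= 160 and D <= 90. Under the amended release, S < 160 rules out the systolic limb as well, so no overlap remains.

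**Enumeration over whole mm Hg pairs** (this tests the rule; it does not estimate how often patients are affected):

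| Band | Pairs | Trigger and release as written | Trigger and release as amended |
|---|---|---|---|
| S 160-220, D 50-90 | 61 x 41 = 2,501 | 2,501 | 0 |
| S 160-220, D 91-99 | 61 x 9 = 549 | 0 | 0 |
| S 160-220, D 100-130 | 61 x 31 = 1,891 | 0 | 0 |
| D 100-130, S above D and at most 159 | 59 + 58 + ... + 29 = 31 x 44 = 1,364 | 0 | 0 |

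The four bands add up to all 6,305 trigger readings on the grid.

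**Examples**

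| Reading | Hold starts | Releasable at once, as written | Releasable at once, as amended |
|---|---|---|---|
| 165/85 | yes | yes | no |
| 200/85 | yes | yes | no |
| 165/95 | yes | no | no |
| 150/102 | yes | no | no |

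A symptomatic patient stays held until symptoms resolve. After that, systolic pressure again plays no part.

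**Comparison with the other Grade 3 holds in Section 6**

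- Table 2, hematologic: "Hold dose until recovery to \leq Grade 2, then resume regorafenib at one lower dose level".
- Table 3, liver function: "Hold dose until \leq Grade 1 for baseline - Grade 1 OR until Grade 2 if baseline was Grade 2".
- Table 4, hand-foot skin reaction: "interrupt regorafenib for a minimum of 7 days and until toxicity resolved to Grade 0-1".
- Table 6, other non-hematologic: "Hold dose until recovery to \leq Grade 2 (for AEs in Cycle 1: resolution to \leq Grade 1").

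Each requires the toxicity to leave Grade 3 before a held dose resumes. Table 5 is the only one whose hold can end while the patient is still Grade 3.

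**Does another rule supply the missing limit?** Section 6.3 is headed as covering other toxicities, and its one-level reduction on restart conflicts with Table 5's same-dose restart, so it cannot be read into Table 5. Exclusion criterion 14 (systolic above 180 or diastolic above 100) applies at entry, not at restart.

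**The case against.** The strongest case is that this is a drafting point with little practical effect.

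- **Treatment and monitoring.** The row requires antihypertensive treatment, and the text above the table calls for close follow-up and effective control. The reduction rule refers to blood pressure in general, so a patient still at 165/85 on new therapy could reasonably be judged uncontrolled and reduced. Nothing compels an investigator to restart at 200/85. All of this stands as mitigation. None of it sets a systolic value for restart, and the reduction depends on a later reading. After the first 6 weeks of regorafenib, the fixed schedule may not supply that reading until the next 28-day cycle.
- **Dosing at Grade 3 elsewhere.** Table 6 footnote b lets certain Grade 3 laboratory findings continue without interruption. That exempts them from the hold, at the investigator's judgement and after mandatory work-up. It does not end a hold at Grade 3.
- **Entry limit.** Criterion 14 admits a patient at 170/85, so a restart limit of 160 is stricter than the starting limit. That is true, and the amendment should make the difference deliberate. It is defensible because Table 5 deals with hypertension that emerges on treatment and 160 is its own Grade 3 boundary. The entry rule also shows that the protocol treats systolic pressure as a risk: 200/85 bars a new patient from starting, yet Table 5 allows a restart there.
- **A diastolic convention.** Diastolic 90 is also the only numeric target in the Grade 2 row. Leaving that row unchanged does not make the Grade 3 correction unsound.
- **Labelling.** Section 8.2 also points to approved labelling and institutional practice. The label is not in the documents, so what it would add cannot be assessed.

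**Conclusion.** The concern holds. In every asymptomatic case with systolic at least 160 and diastolic at most 90 mm Hg, the hold as written starts and can end at the same reading, with restart at the same dose level. The defect is limited to the systolic trigger: holds triggered by diastolic pressure, and readings with diastolic 91 to 99, behave as intended.

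The conclusion rests on reading the release cell literally. How many patients are affected cannot be stated. Hypertension is not in the stopping rules, so those are untouched. This should be corrected at the next amendment because the stated rule gives a wrong result for identifiable patients and the correction is small.

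**What to change.** In the Grade 3 row of Table 5, add a systolic condition to the release cell and to the treatment-aim cell: at minimum systolic below 160 mm Hg together with diastolic at most 90. The sponsor's clinical team may choose a stricter systolic limit.

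In the same edit, state whether a hold applies when Grade 3 is met only because more intensive therapy is indicated, since a pressure limit does not settle that case.

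The cost is two cells of one table row, plus that clarification, and no new data. Some holds will last longer and count toward the 4-week limit in footnote a, so a few more patients may go off protocol therapy.
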